#### 6.3.1.1 Stratification

No stratification based on age, sex or other characteristics will be used in this study.

#### 6.3.2 Blinding

This study is an open-label study; therefore, the Sponsor, investigator and participant will know the treatment administered.

See Section 8.1.10 for a description of the method of unblinding a participant during the study, should such action be warranted.

## 6.4 Treatment Compliance

Interruptions from the protocol specified treatment plan for greater than 12 weeks between pembrolizumab doses require consultation between the investigator and the Sponsor and written documentation of the collaborative decision on participant management.

## 6.5 Concomitant Therapy

Medications or vaccinations specifically prohibited in the exclusion criteria are not allowed during the ongoing study. If there is a clinical indication for any medication or vaccination specifically prohibited, discontinuation from study treatment may be required. The investigator should discuss any questions regarding this with the Sponsor Clinical Director. The final decision on any supportive therapy or vaccination rests with the investigator and/or the participant's primary physician. However, the decision to continue the participant on study treatment requires the mutual agreement of the investigator, the Sponsor and the participant.

### 6.5.1 Acceptable Concomitant Therapy

All treatments that the investigator considers necessary for a participant's welfare may be administered at the discretion of the investigator in keeping with the community standards of medical care. All concomitant medication will be recorded on the case report form (CRF) including all prescription, over-the-counter (OTC), herbal supplements, and IV medications and fluids. If changes occur during the trial period, documentation of drug dosage, frequency, route, and date may also be included on the CRF.

All concomitant medications received within 30 days before the first dose of trial treatment and 30 days after the last dose of trial treatment should be recorded. Concomitant medications administered after 30 days after the last dose of trial treatment should be recorded for SAEs and ECIs as defined in Section 8.4.

### 6.5.2 Prohibited Concomitant Therapy

Participants are prohibited from receiving the following therapies during the Screening and Treatment Phase (including retreatment for post-complete response relapse) of this trial:

- Antineoplastic systemic chemotherapy or biological therapy not specified in this protocol
- Immunotherapy not specified in this protocol
- Investigational agents other than pembrolizumab
- Radiation therapy

*Note: Radiation therapy to a symptomatic lesion or to the brain may be considered on an exceptional case by case basis after consultation with Sponsor. The participant must have clear measurable disease outside the radiated field. Administration of palliative radiation therapy will be considered clinical progression for the purposes of determining PFS.*

- Live vaccines within 30 days prior to the first dose of trial treatment and while participating in the trial. Examples of live vaccines include, but are not limited to, the following: measles, mumps, rubella, chickenpox, yellow fever, rabies, BCG, and typhoid (oral) vaccine. Seasonal influenza vaccines for injection are generally killed virus vaccines and are allowed. However, intranasal influenza vaccines (e.g. FluMist®) are live attenuated vaccines, and are not allowed.

- Systemic glucocorticoids for any purpose other than to modulate symptoms from events of suspected immunologic etiology. The use of glucocorticoids for AEs not attributed to pembrolizumab is allowed with approval from the Sponsor. Physiologic doses of corticosteroids (not exceeding 10 mg of prednisone equivalent daily) are allowed.

*Note: Inhaled steroids are allowed for management of asthma.*

Participants who, in the assessment by the investigator, require the use of any of the aforementioned treatments for clinical management should be removed from the trial. Participants may receive other medications that the investigator deems to be medically necessary.

The Exclusion Criteria describe other medications that are prohibited in this trial.

There are no prohibited therapies during the Post-Treatment Follow-up Phase.

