## **7. Discontinuation of Study Treatment and Participant Withdrawal**

### **7.1 Discontinuation of Study Treatment**

Discontinuation of study treatment does not represent withdrawal from the study.

As certain data on clinical events beyond study treatment discontinuation may be important to the study, they must be collected through the participant's last scheduled follow-up, even if the participant has discontinued study treatment. Therefore, all participants who discontinue study treatment prior to completion of the protocol-specified treatment period will still continue to participate in the study as specified in Section 1.3 and Section 8.10.3.

Participants may discontinue study treatment at any time for any reason or be discontinued from the study treatment at the discretion of the investigator should any untoward effect occur. In addition, a participant may be discontinued from study treatment by the investigator or the Sponsor if study treatment is inappropriate, the study plan is violated, or for administrative and/or other safety reasons. Specific details regarding procedures to be performed at study treatment discontinuation are provided in Section 8.1.9.

A participant must be discontinued from study treatment but continue to be monitored in the study for any of the following reasons:

- The participant or participant's legally acceptable representative requests to discontinue study treatment.
- Radiographic disease progression as determined by local/site assessment

Note: For unconfirmed radiographic disease progression, or confirmed progression with reduction in disease burden from baseline please see Section 8.2.1.4

- Any progression or recurrence of any malignancy, or any occurrence of another malignancy that requires active treatment
- Noncompliance with study treatment or procedure requirements
- Recurrent Grade 2 pneumonitis

- Unacceptable AEs as described in Section 6.6
- Intercurrent illness that prevents further administration of study treatment
- The participant has a confirmed positive serum pregnancy test
- Investigator's decision to withdraw the participant
- The participant is lost to follow-up (Section 7.3)
- Completed 35 cycles (~2 years) of treatment with pembrolizumab
- Administrative reasons

For participants who are discontinued from study treatment but continue to be monitored in the study, see Section 1.3 and Section 8.10.3 for those procedures to be completed at each specified visit.

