## **7.2 Participant Withdrawal From the Study**

A participant must be withdrawn from the study if the participant or participant's legally acceptable representative withdraws consent from the study.

If a participant withdraws from the study, they will no longer receive study treatment or be followed at scheduled protocol visits.

Specific details regarding procedures to be performed at the time of withdrawal from the study, as well as specific details regarding withdrawal from future biomedical research are outlined in Section 8.1.9. The procedures to be performed should a participant repeatedly fail to return for scheduled visits and/or if the study site is unable to contact the participant are outlined in Section 7.3.

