### **8.10.3.3 Survival Follow-up**

Participants who experience confirmed disease progression or start a new anticancer therapy, will move into the Survival Follow-Up Phase and should be contacted by telephone approximately every 12 weeks to assess for survival status until death, withdrawal of consent, or the end of the trial, whichever occurs first.

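### Section 6.5.2 removes on-treatment participants who need a prohibited therapy from the trial, contradicting the rules that keep them in follow-up; read literally, it loses survival data

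*Combined protocol and SAP*

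**What the plan says.** Section 6.5.2 lists therapies prohibited during the Screening and Treatment Phase: systemic antineoplastic and biological therapy, other immunotherapy, other investigational agents, radiation, live vaccines, and systemic glucocorticoids outside stated exceptions. Participants who, in the investigator's assessment, "require the use of any of the aforementioned treatments for clinical management should be removed from the trial". The section closes by stating that nothing is prohibited in post-treatment follow-up.

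Other places treat the same participant differently:

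- **Section 6.5**, the parent section: "If there is a clinical indication for any medication or vaccination specifically prohibited, discontinuation from study treatment may be required". It does not mention leaving the trial.
- **Section 7.1:** "Discontinuation of study treatment does not represent withdrawal from the study", and "all participants who discontinue study treatment prior to completion of the protocol-specified treatment period will still continue to participate in the study".
- **Section 7.2:** "A participant must be withdrawn from the study if the participant or participant's legally acceptable representative withdraws consent from the study". The consequence of withdrawal is that "If a participant withdraws from the study, they will no longer receive study treatment or be followed at scheduled protocol visits".
- **Section 8.10.3.3:** participants who have confirmed progression or "start a new anticancer therapy, will move into the Survival Follow-Up Phase", with telephone contact about every 12 weeks.
- **Synopsis (1.1):** all participants are followed by telephone for OS until death, withdrawal of consent or the end of the study.

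**The concern.** The protocol separates stopping study treatment from leaving the study. The instruction in 6.5.2 uses neither of those terms, and its plain meaning is leaving the study. A site that acts on it stops survival contact for a participant whom 7.1, 8.10.3.3 and the synopsis keep in follow-up.

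What is at stake is mainly OS, a secondary endpoint. The main OS analysis in section 9.6.2 follows participants through new anticancer treatment; only the sensitivity analysis censors there. Kaplan-Meier estimation assumes that censoring is unrelated to prognosis. A participant who needs chemotherapy, another immunotherapy or radiation while still on study treatment plausibly has a worse outlook than one who does not, so removal at that point would probably bias OS upward. It would also hide deaths from the count that sets the date of the final OS analysis (section 9.7).

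**Working it through.** **1. Who is covered by 6.5.2.** The prohibition runs only through the Screening and Treatment Phase. A participant who stops pembrolizumab for progression under 7.1 and then starts next-line therapy has already left that phase, so 6.5.2 does not apply. The conflict concerns participants still in the Treatment Phase who need a listed therapy. The section's own exceptions narrow this group further:

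- Steroids are allowed for suspected immune-related events, at physiologic doses, by inhalation for asthma and, with Sponsor approval, for other adverse events.
- Radiation to a symptomatic lesion or the brain may be considered case by case after consultation with the Sponsor.

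**2. Which texts conflict, by trigger.**

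| Trigger while on treatment | 6.5.2 | Conflicting text |
|---|---|---|
| New systemic anticancer therapy | Leaves the trial | 6.5, 7.1, 8.10.3.3, synopsis |
| Non-exempt steroid, live vaccine | Leaves the trial | 6.5, 7.1, 8.10.3.2, synopsis (8.10.3.3 does not cover these) |
| Radiation without an agreed exception | Leaves the trial | 6.5, 7.1, synopsis; 8.10.3.3 if it counts as new anticancer therapy |

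**3. PFS.** Section 9.6.2 censors PFS at the last assessment before new anticancer treatment, and 8.10.3.2 ends the disease-status effort there. For new systemic anticancer therapy before progression, the PFS record is therefore the same with or without removal. A participant who has already progressed already has the event. Loss is possible only for non-exempt steroids, live vaccines and perhaps palliative radiation. Radiation is uncertain because 6.5.2 counts it as progression for PFS, whereas 9.6.2 counts only RECIST 1.1 progression or death.

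**4. Death trigger.** Section 9.7 sets the final OS analysis at about 70% of participants dead: 0.70 × 60 = 42, which reproduces the stated figure. If r participants leave and their deaths are not seen, the death rate needed among the rest is 42/(60 − r). The values of r are assumed.

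| Removed, r | Needed among the rest | Unseen deaths if 70–90% of those removed die (assumed) |
|---|---|---|
| 6 (10%) | 42/54 = 77.8% | 4.2–5.4 |
| 12 (20%) | 42/48 = 87.5% | 8.4–10.8 |
| 18 (30%) | 42/42 = 100% | 12.6–16.2 |

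**5. OS bias, first illustration.** All inputs are assumed: exponential survival with median 24 months; a fraction of participants removed, if still alive, at a time uniform on 2–9 months; hazard afterwards multiplied by 1, 2 or 3. Kaplan-Meier with removal is compared with complete follow-up, by simulation.

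| Fraction removed | True 24-month OS (hazard ×2 / ×3) | Kaplan-Meier with removal | True median, months (×2 / ×3) | Estimated median, months |
|---|---|---|---|---|
| 10% | 48% / 47% | about 50% | 22.6 / 21.8 | about 24 |
| 20% | 46% / 43% | about 50% | 21.4 / 19.8 | about 24 |
| 30% | 44% / 40% | about 50% | 20.3 / 18.1 | about 24 |

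With a multiplier of 1 there is no bias, only fewer observed deaths.

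**6. OS bias, second illustration.** All inputs are assumed: median time to progression 6 months, 90% of first events are progression, median survival after progression 12 months. If 5% or 10% of progressors are censored at progression, 24-month OS moves from 40.0% to about 40.4% or 40.9%, and the median from 19.4 to 19.6 or 19.9 months. For scale, the simple 95% half-width at 40% with 60 participants and no censoring is 1.96 × √(0.4 × 0.6/60) = 0.124, about 12 points.

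**The case against.** The strongest reply is that 6.5.2 was meant to say removal from study treatment. Its parent section says so, the synopsis commits to OS follow-up for all participants, and the absence of any prohibition in post-treatment follow-up presupposes that such participants remain under observation. Section 8.10.3.4 also lets the Sponsor request survival status at any time, and Amendment 04 says the study is closing, so a prospective wording change protects little. All of this stands as a reason to expect limited harm. It does not remove the instruction, which sites may act on as written, and a survival request reaches a removed participant only if the site still treats that person as a participant.

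A reader might infer several stronger conclusions that the documents do not support:

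- **A quarter or half of progressors are lost to OS.** No removal rate is given, and the usual sequence of progression, stopping, then next-line therapy is outside 6.5.2.
- **PFS is lost as OS is.** Section 9.6.2 already censors before new anticancer treatment.
- **Any steroid or radiation use means removal.** The exceptions in 6.5.2 say otherwise.
- **The primary comparisons are distorted, because participants removed before the first scan become non-responders.** The missing-data rule in 9.6.2 is written for ORR estimation, a participant deteriorating that early would probably be a non-responder anyway, and no effect has been shown.
- **Section 7.2 makes withdrawal of consent the only way out.** It says withdrawal of consent requires leaving, not that nothing else can. The firmer support is the synopsis, whose listed ends to OS follow-up do not include needing a prohibited therapy.

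**Conclusion.** The contradiction is real: 6.5.2 cannot be followed literally together with 6.5, 7.1, 8.10.3.3 and the synopsis. Followed literally, it ends survival follow-up for participants still in the Treatment Phase who need a listed therapy, adds censoring to the main OS analysis, and leaves deaths uncounted towards the trigger.

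The direction, OS probably biased upward, rests on removed participants having a worse prognosis. That is plausible for those needing further anticancer therapy or radiation, but the documents do not state it. The size cannot be determined from the documents. Under the assumptions shown, small removal fractions (5–10%) move 24-month OS by roughly half a point to three points, well inside the sampling error of 60 participants; 20–30% with a two- to threefold hazard would move it by about 4 to 10 points. This is an inconsistency in the instructions that should be corrected for the sake of a secondary endpoint. It does not undermine the primary analyses.

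**What to change.** 1. Reconcile 6.5, 6.5.2 and 7.1 on what happens to study treatment when a prohibited therapy is needed. That choice is the sponsor's, and none is proposed here.
2. For data collection, replace the removal wording in 6.5.2 with a reference to follow-up under 7.1 and 8.10.3. State that OS follow-up ends only at death, withdrawal of consent or the end of the study, as the synopsis has it.
3. Before the OS analysis, identify anyone already removed under 6.5.2 who did not withdraw consent, and obtain survival status through the request procedure in 8.10.3.4. With the study closing, this is the most useful step.
4. While these sections are open, reconcile 6.5.2 with 9.6.2 on whether palliative radiation is a PFS event.

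The cost is a sentence or two in an amendment or site letter and one round of survival queries. The follow-up procedures already exist.

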### **6.5.3 Rescue Medications and Supportive Care**

Participants should receive appropriate supportive care measures as deemed necessary by the treating investigator. Suggested supportive care measures for the management of AEs with potential immunologic etiology are outlined along with the dose modification guidelines in Section 6.6.1, [Table 3](#). Where appropriate, these guidelines include the use of oral or IV treatment with corticosteroids, as well as additional anti-inflammatory agents if symptoms do not improve with administration of corticosteroids. Note that several courses of steroid tapering may be necessary as symptoms may worsen when the steroid dose is decreased. For each disorder, attempts should be made to rule out other causes such as metastatic disease or bacterial or viral infection, which might require additional supportive care. The treatment guidelines are intended to be applied when the Investigator determines the events to be related to pembrolizumab.

Note: If after the evaluation of the event, it is determined not to be related to pembrolizumab, the Investigator does not need to follow the treatment guidance. Refer to [Table 3](#) in Section 6.6.1 for guidelines regarding dose modification and supportive care.

It may be necessary to perform conditional procedures such as bronchoscopy, endoscopy, or skin photography as part of evaluation of the event.

## 6.6 Dose Modification

### 6.6.1 Dose Modification and Toxicity Management for Immune-related AEs Associated With Pembrolizumab

AEs associated with pembrolizumab exposure may represent an immunologic etiology. These immune-related AEs (irAEs) may occur shortly after the first dose or several months after the last dose of pembrolizumab treatment and may affect more than one body system simultaneously. Therefore, early recognition and initiation of treatment is critical to reduce complications. Based on existing clinical study data, most irAEs were reversible and could be managed with interruptions of pembrolizumab, administration of corticosteroids and/or other supportive care. For suspected irAEs, ensure adequate evaluation to confirm etiology or exclude other causes. Additional procedures or tests such as bronchoscopy, endoscopy, skin biopsy may be included as part of the evaluation. Based on the severity of irAEs, withhold or permanently discontinue pembrolizumab and administer corticosteroids. Dose modification and toxicity management guidelines for irAEs associated with pembrolizumab are provided in [Table 3](#).

Table 3 Dose Modification and Toxicity Management Guidelines for Immune-related AEs Associated with Pembrolizumab

General instructions:				
irAEs	Toxicity grade or conditions (NCI CTCAE v4.0)	Action taken to pembrolizumab	irAE management with corticosteroid and/or other therapies	Monitor and follow-up
Pneumonitis	Grade 2	Withhold	
 
Administer corticosteroids (initial dose of 1-2 mg/kg prednisone or equivalent) followed by taper
 
	
 
Monitor participants for signs and symptoms of pneumonitis
 
Evaluate participants with suspected pneumonitis with radiographic imaging and initiate corticosteroid treatment
 
Add prophylactic antibiotics for opportunistic infections
 

	Grade 3 or 4, or recurrent Grade 2	Permanently discontinue		
Diarrhea / Colitis	Grade 2 or 3	Withhold	
 
Administer corticosteroids (initial dose of 1-2 mg/kg prednisone or equivalent) followed by taper
 
	
 
Monitor participants for signs and symptoms of enterocolitis (ie, diarrhea, abdominal pain, blood or mucus in stool with or without fever) and of bowel perforation (ie, peritoneal signs and ileus).
 
Participants with <math>\geq</math>Grade 2 diarrhea suspecting colitis should consider GI consultation and performing endoscopy to rule out colitis.
 
Participants with diarrhea/colitis should be advised to drink liberal quantities of clear fluids. If sufficient oral fluid intake is not feasible, fluid and electrolytes should be substituted via IV infusion.
 

	Grade 4	Permanently discontinue		

irAEs	Toxicity grade or conditions (NCI CTCAE v4.0)	Action taken to pembrolizumab	irAE management with corticosteroid and/or other therapies	Monitor and follow-up
AST / ALT elevation or Increased bilirubin	Grade 2	Withhold	
 
Administer corticosteroids (initial dose of 0.5-1 mg/kg prednisone or equivalent) followed by taper
 
	
 
Monitor with liver function tests (consider weekly or more frequently until liver enzyme value returned to baseline or is stable)
 

	Grade 3 or 4	Permanently discontinue	
 
Administer corticosteroids (initial dose of 1-2 mg/kg prednisone or equivalent) followed by taper
 
	
Type 1 diabetes mellitus (T1DM) or Hyperglycemia	Newly onset T1DM or Grade 3 or 4 hyperglycemia associated with evidence of $\beta$ -cell failure	Withhold	
 
Initiate insulin replacement therapy for participants with T1DM
 
Administer anti-hyperglycemic in participants with hyperglycemia
 
	
 
Monitor participants for hyperglycemia or other signs and symptoms of diabetes.
 

Hypophysitis	Grade 2	Withhold	
 
Administer corticosteroids and initiate hormonal replacements as clinically indicated.
 
	
 
Monitor for signs and symptoms of hypophysitis (including hypopituitarism and adrenal insufficiency)
 

	Grade 3 or 4	Withhold or permanently discontinue 		
Hyperthyroidism	Grade 2	Continue	
 
Treat with non-selective beta-blockers (eg, propranolol) or thionamides as appropriate
 
	
 
Monitor for signs and symptoms of thyroid disorders.
 

	Grade 3 or 4	Withhold or permanently discontinue 		
Hypothyroidism	Grade 2-4	Continue	
 
Initiate thyroid replacement hormones (eg, levothyroxine or liothyroinine) per standard of care
 
	
 
Monitor for signs and symptoms of thyroid disorders.
 

irAEs	Toxicity grade or conditions (NCI CTCAE v4.0)	Action taken to pembrolizumab	irAE management with corticosteroid and/or other therapies	Monitor and follow-up
Nephritis and Renal dysfunction	Grade 2	Withhold	
 
Administer corticosteroids (prednisone 1-2 mg/kg or equivalent) followed by taper.
 
	
 
Monitor changes of renal function
 

	Grade 3 or 4	Permanently discontinue		
Myocarditis	Grade 1 or 2	Withhold	
 
Based on severity of AE administer corticosteroids
 
	
 
Ensure adequate evaluation to confirm etiology and/or exclude other causes
 

	Grade 3 or 4	Permanently discontinue		
All other irAEs	Intolerable/ persistent Grade 2	Withhold	
 
Based on type and severity of AE administer corticosteroids
 
	
 
Ensure adequate evaluation to confirm etiology and/or exclude other causes
 

	Grade 3	Withhold or discontinue based on the type of event. Events that require discontinuation include and not limited to: Guillain-Barré Syndrome, encephalitis		
	Grade 4 or recurrent Grade 3	Permanently discontinue		

Abbreviations: AE = adverse event; ALT = alanine aminotransferase; AST = aspartate aminotransferase; CTCAE = Common Terminology Criteria for Adverse Events; GI = gastrointestinal; irAE = immune-related adverse event; IV = intravenous; NCI = National Cancer Institute; T1DM = type 1 diabetes mellitus.

- Withhold or permanently discontinue pembrolizumab is at the discretion of the investigator or treating physician.

